5.4. Baseline HF and patient characteristics

The following baseline cluster (HF) characteristics will be summarized by study arm:

- HF type (dispensary or health center) and region
- Access to GoT-HoMIS
- Average number of patients under 15 seen per month by HF
- Baseline % antibiotic prescription by HF (as reported in ePOCT+) in the month before the start of the study (May 2023)

The baseline patient characteristics that will be summarized by study arm, and for the overall study include:

- Demographics: sex (number and percentage); age (median and IQR), age groups 0-2 months, 2 months - 5 years, 5-14 years (number and percentage) (for all included participants)
- Medical history: Main reasons for consultation - fever, respiratory, gastrointestinal, ear/nose/throat/mouth or skin complaint (number and percentage) (for participants with ePOCT+ data)
- Basic measurements: weight for age (median and IQR) (for participants with ePOCT+ data)

No formal statistical comparisons of baseline data will be performed.

6. Analysis

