6.1. Outcome definition

6.1.1. Primary outcome

Percentage of children prescribed an antibiotic in the intervention group (medAL-mentor) as compared to the control group (routine monitoring)

Outcome measure: Number of children for whom at least one systemic (oral or parenteral) antibiotic has been prescribed during consultation, over all eligible children, as reported by the HCWs in the routine registry

Timing and method of assessment: documented by the HCW at the end of the consultation, in the routine registry (day 0)

Analysis type: superiority

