6.1.2. Secondary outcomes

All secondary outcomes are compared between the intervention (medAL-mentor) and control (routine care) arms (superiority analysis).

a. Uptake of ePOCT+

Percentage of consultations with eligible children performed with ePOCT+

Outcome measure: number of consultations completed with ePOCT+, over all consultations with eligible children as reported in MTUHA books

Timing and method of assessment: documented by the HCW during the consultation (medAL-reader) and at the end of the consultation (routine registry), at day 0

Analysis type: superiority

b. Quality of care indicators

• Percentage of children in whom key signs have been checked by HCWs

Number of children in whom each of the key signs (temperature, weight, MUAC, respiratory rate) has been checked by HCWs, over the total number of children for whom this was recommended, as reported by HCWs in ePOCT+

Timing and method of assessment: documented by the HCW during the consultation (medAL-reader) at day 0

Analysis type: superiority

- **Percentage of children for whom appropriate diagnostic tests have been performed by HCWs**

Number of children for whom each of the diagnostic tests (haemoglobin and malaria tests) has been performed by HCWs, over the total number of children for whom the diagnostic test was recommended, as reported by HCWs in ePOCT+

Timing and method of assessment: documented by the HCW during the consultation (medAL-reader) at day 0

Analysis type: superiority

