6.2. Analysis methods

Analyses will follow CONSORT guidelines.¹⁹

All the analyses will be carried out using generalized linear mixed models (GLMM, more specifically the multilevel logistic regression model with fixed and random-effects) to account for the complex multi-level structure of the data (induced by the stratified cluster randomized procedure), with individuals measurements nested within HCWs, who are themselves nested within HFs, which in turn are nested within districts, and at the highest-level districts are nested

within regions.²⁰ For the primary outcome, available risk factors at the individual level will be age category, sex, and type of final diagnosis (gastro-intestinal, respiratory, skin, malaria, other). For secondary outcomes, available risk factors at the individual level will be age, sex, child presenting with fever, gastro-intestinal, respiratory, ear/nose/throat/mouth and/or skin problem. In addition, to account for the correlation between the two exposure groups induced by the stratification, all the analyses will be adjusted for the stratification factors used in the randomization and not already accounted for (i.e. attendance rate and use of GoT-HoMIS) in the multi-level structure. Finally, the analyses will be adjusted by the baseline antibiotic prescription at each HF.

A special random-effects structure will be used at the HF level to account for unmeasured heterogeneity of the intervention effect²¹ and confounding by cluster will be dealt with by separating within- and between-cluster effects using a partitioning method.^{22,23}

Interactions (i.e. effect modification) between covariables (at the individual level) and exposure (i.e. medAL-mentor vs control) will be introduced into the model as fixed-effects. Variable selection will be based on clinical relevance and not on statistical tests of significance; consequently, no correction for multiple testing will be applied.²⁴

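### The key-sign and diagnostic-test outcomes are adjusted for baseline antibiotic prescribing but not for their own May 2023 facility level, which ePOCT+ can supply

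*SAP*

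**What the plan says.** SAP section 6.2 puts every outcome into one modelling framework: "All the analyses will be carried out using generalized linear mixed models". It lists separate individual-level risk factors for the primary and the secondary outcomes, and adds the stratification factors. It then closes the paragraph with a single baseline covariate for all of them: "Finally, the analyses will be adjusted by the baseline antibiotic prescription at each HF".

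Section 5.4 defines that baseline as "Baseline % antibiotic prescription by HF (as reported in ePOCT+) in the month before the start of the study (May 2023"). No other baseline measure of facility performance is listed there.

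Section 6.1.2 gives the secondary outcomes and their sources:

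- **Key signs:** the numerator is defined as "Number of children in whom each of the key signs (temperature, weight, MUAC, respiratory rate) has been checked by HCWs". The denominator is limited to children whom the tool advised to have that sign checked, and both counts come from ePOCT+ entries.
- **Diagnostic tests** (haemoglobin, malaria): the count of tested children is taken "over the total number of children for whom the diagnostic test was recommended, as reported by HCWs in ePOCT". Both parts again come from the tool.
- **Uptake:** the numerator is the count of finished tablet consultations, but the denominator comes from the registry: "over all consultations with eligible children as reported in MTUHA books".

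**The concern.** Facilities are the randomized units, 20 per arm. When clusters are large, nearly all the variance of an arm comparison lies between facilities. Enrolling more children then helps little, while a good facility-level predictor helps a lot. The natural predictor of how often a facility weighs children or does haemoglobin tests during follow-up is how often it did so just before the start. A facility's antibiotic percentage does not measure those practices directly.

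Section 5.4 presupposes that ePOCT+ was recording in these facilities in May 2023. For key signs and tests, the better-matched covariate can therefore come from a source that the plan already uses. If it is left out, the secondary comparisons may have wider intervals than necessary and be more exposed to a chance difference in starting level between arms.

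**Working it through.** **Inputs from SAP 3.2:** ICC 0.08 for antibiotic prescription, 40% in control, a 15-point reduction, 80 patients per month for 6 months (480 per facility), coefficient of variation of cluster size 0.6, 80% power, two-sided alpha 0.05, 20 facilities per arm. The SAP gives no ICC for any secondary outcome and no facility-level correlation between May and follow-up. Both are assumptions below.

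**1. The plan's own figure.** For 40% against 25%, individual randomization needs 152 per arm. The design effect for equal clusters is 1 + 479 × 0.08 = 39.32. Then 152 × 39.32 / 480 = 12.45, so 13 clusters and 13 × 480 = 6240 per arm, as stated. Allowing for the coefficient of variation through the relative-efficiency formula gives a design effect of 39.65 and 12.55 clusters, again 13. This figure concerns the primary outcome and does not settle the present point. It does confirm the inputs.

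**2. Between-facility share of variance.** 480 × 0.08 / (480 × 0.08 + 0.92) = 38.4 / 39.32 = 0.977, about 98%. This holds only if a secondary outcome has the same ICC and the full 480 children.

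**3. Gain from the outcome's own baseline, against no baseline covariate.** In an analysis of facility means, the variance of the arm effect is multiplied by 1 − r². Here r = true correlation × √(reliability of May value × reliability of follow-up mean), and reliability = m × ICC / (1 + (m − 1) × ICC).

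At ICC 0.08 the reliabilities are 6.4 / 7.32 = 0.874 (m = 80) and 38.4 / 39.32 = 0.977 (m = 480). The square root of their product is 0.924.

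| True correlation | Observed r | Variance reduction: ICC 0.08, 80 / 480 children | ICC 0.08, 20 / 120 | ICC 0.02, 20 / 120 |
|---|---|---|---|---|
| 0.3 | 0.28 | 8% | 5% | 2% |
| 0.5 | 0.46 | 21% | 15% | 5% |
| 0.7 | 0.65 | 42% | 28% | 10% |
| 0.9 | 0.83 | 69% | 47% | 17% |

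The observed r shown is for the 80 / 480 column.

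For an outcome near 50% with 80 / 480 children, the variance of a facility mean is 0.25 × (0.08 + 0.92/480) = 0.0205. The difference detectable with 80% power is then (2.024 + 0.851) × √(2 × 0.0205 / 20) = 13.0 points without a baseline covariate. With the own baseline it is 12.5, 11.5, 9.9 and 7.2 points down the rows.

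**4. Swapping the antibiotic covariate for the own baseline.** If the antibiotic baseline correlates q with the outcome, the variance ratio (own baseline over antibiotic baseline) is (1 − r²) / (1 − q²).

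- At r = 0.46 it is 0.79, 0.82 and 0.94 for q = 0, 0.2 and 0.4.
- At r = 0.28 and q = 0.4 it is 0.9216 / 0.84 = 1.10, so a swap would lose precision.

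**5. Adding the own baseline and keeping the antibiotic one.** In large samples this cannot lose. With 40 facilities there is a small price. The t critical value moves from 2.024 to 2.026 for each extra cluster-level covariate. In addition, a covariate that predicts nothing inflates the expected variance through its own chance imbalance. With two arms and p covariates the factor is 37 / (37 − p), so going from one covariate to two costs 36/35 = 1.029, about 3%. At the bottom of the table (2%) the addition roughly breaks even; from about 5% upward it gains.

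**The case against.** The case on the other side is substantial, and much of it stands.

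- **Validity is not at issue.** Facilities are randomized, so the planned analysis is unbiased and its intervals already allow for chance imbalance. The SAP claims no power for secondary outcomes. A reader might infer that these comparisons are flawed; the documents do not support that.
- **Uptake is different.** A reader might infer that ePOCT+ already holds every secondary baseline. It does not hold the uptake denominator, which is in the MTUHA books, and the SAP does not mention extracting May registry counts.
- **The size is assumed.** The ICC of 0.08 belongs to antibiotic prescribing. Key-sign and test outcomes count only consenting children managed with ePOCT+ for whom the item was recommended, so 80 and 480 are upper figures if attendance is as assumed, and the 98% share is not established for them. The SAP's multilevel logistic model, with individual risk factors, stratification factors and further levels, may already absorb some between-facility variance. No single percentage can be quoted.
- **The antibiotic baseline suits many exploratory outcomes.** Five of the six respiratory and diarrhoea outcomes in section 6.1.3 are antibiotic prescriptions. Others use the registry or may have very few May cases. A facility with no May denominator has an undefined covariate and, with no imputation (section 6.3), would drop out of the model.

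What these objections leave untouched is the narrow point. For key signs and tests, the plan names no own baseline although the records needed for it come from a source that it already uses.

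**Conclusion.** The point holds for the key-sign and diagnostic-test outcomes, as a matter of efficiency. Section 6.2 leaves available precision unused there. The gain is a range: about 8% to 69% of the variance against no baseline covariate, under ICC 0.08, 80 and 480 children per facility and true correlations of 0.3 to 0.9. It can be as little as 2% with ICC 0.02 and 20 and 120 children, where the cost of an extra covariate cancels it. Against the planned antibiotic covariate, the gain also depends on how well that covariate predicts the outcome, which the documents do not say.

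It would go too far to say that the plan loses precision for nothing, or that the antibiotic covariate should be replaced. The first needs correlations that the documents do not give. The second can lose precision, as step 4 shows. Confidence is high on what the SAP says and moderate on how much would be gained.

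**What to change.** In section 6.2, state before outcome data are seen that each key-sign outcome (temperature, weight, MUAC, respiratory rate) and each test outcome (haemoglobin, malaria) is additionally adjusted for that outcome's facility-level value in May 2023 from ePOCT+, and that the antibiotic baseline is kept. List these baselines by arm in section 5.4. Say what is done if a facility has no May denominator for an outcome; falling back to the planned covariates for that outcome would keep all 40 facilities in.

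For uptake, do the same only if May 2023 MTUHA counts are extracted: completed ePOCT+ consultations over registry consultations with eligible children. Otherwise leave the planned adjustment.

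For the exploratory outcomes, make no general rule. Those on antibiotic prescription, those based on the registry and those with sparse denominators should stay with the planned covariate.

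The cost is a few lines of SAP text, one extra extract of May ePOCT+ data, and one cluster-level degree of freedom per model, with the roughly 3% variance price shown above if the baseline turns out to be uninformative. Uptake would also need one month of registry counts. If outcome data have already been examined, the own-baseline models should be labelled as post hoc sensitivity analyses.
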